This project will contribute toward determining whether these potentially beneficial properties of nebivolol, known to improve diastolic dysfunction, will also improve PH severity in patients with HFpEF. This contribution will be important because it could uncover a potential treatment for a disease category that currently has no accepted treatments. If nebivolol significantly improves PH severity in patients with HFpEF, it can be further researched as a probable treatment. Furthermore, this project should also advance knowledge of the hemodynamic effects of chronic nebivolol treatment in HFpEF patients, as very few clinical studies have measured hemodynamics by right heart catheterization both before and after chronic oral treatment.

Methods

This project will be a prospective, open-label four-month clinical pilot study of 40 patients with PH and HFpEF. Patients will be started at 2.5 mg of nebivolol by mouth daily if they were not taking a beta-blocker at enrollment, and titrated up to 10 mg daily, as tolerated. Patients who cannot tolerate a dose increase will continue on the maximum tolerated dose throughout the study. Patients already on a beta-blocker at enrollment will begin on 5 mg and will be titrated to 10 mg daily. DNA and RNA will be collected for genomic studies of disease and drug response. All study procedures will occur at either the UF Clinical Research Center (CRC) or Shands Hospital.

Test/Procedure	Visit 1/1A (wk 0-1)	Call 1 (wk 1)	Call 2 (wk 2)	Visit 2 (wk 4)	Call 3 (wk 5)	Visit 3 (wk 8)	Call 4 (wk 9)	Visit 4 (wk 18)
right heart catheterization	X*							X
transthoracic echo	X*							X
electrocardiogram	X			X		X		X
6-minute walk distance	X			X		X		X
vital signs	X			X		X		X
dyspnea index	X			X		X		X
complete blood count	X			X		X		X
INR	X					X		X
liver function test	X			X		X		X
basic metabolic panel	X			X		X		X
nt-proBNP	X					X		X
RNA collection	X			X		X		X
DNA collection				X		X		
serum collection	X			X		X		X
change in nebivolol dose	X		X	X				X
adverse effect assessment		X	X		X		X	
medication history	X			X		X		X

* = if not done within previous 3 months as part of clinical care

Visit 1 (week 0):

- Blood sample: 2x 8 mL PAXgene (RNA), 1x 10mL lavender top (plasma and PBMCs), 1x 3mL lavender top (CBC with diff), 2x 4mL Li Heparin (nt-proBNP, CMP), 1x2.7mL blue top (INR)
- Vital signs: blood pressure, pulse, respirations, height, weight, etc.
- Dyspnea index
- 6-minute walk test
- Medication history
- EKG

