- Patients will be asked to take oral nebivolol 2.5 mg (or 5 mg) once daily until Visit 2 (**if visit 1A is not needed**). Instruct patient to discontinue previous beta-blocker and begin nebivolol today if they have not taken any beta-blocker today, and tomorrow if they have already taken a beta-blocker today.
- Place note in medical record documenting name of study, responsible physician, procedures, and medication dose.
- If possible, schedule Visit 1A or Visit 2.
- Once complete, provide patient with compensation (\$50).

Visit 1A – IF NEEDED (week 0-1):

- If the patient has not received a two-dimensional transthoracic echocardiogram (TTE) within 3 months of enrollment, it will be done for research purposes, possibly on the same day as visit 1.
- If the patient has not received a right heart catheterization (RHC) within 3 months of enrollment, it will be done for research purposes (Appendix 1).
- Patients will be asked to take oral nebivolol 2.5 mg (or 5 mg) once daily until Visit 2. Instruct patient to discontinue previous beta-blocker and begin nebivolol today if they have not taken any beta-blocker today, and tomorrow if they have already taken a beta-blocker today.
- Once complete, provide patient with compensation (\$200).

Phone Call 1 (week 1):

- How does patient feel compared to before starting study drug?
- Any perceived side effects?
- If not done already, schedule Phone Call 2

Phone Call 2 – IF NEEDED (week 2):

- How does patient feel compared to before starting study drug?
- Any perceived side effects?
- If tolerated, increase nebivolol dose to 5 mg (after approval by study physician)
- If not done already, schedule Visit 2.

Visit 2 (week 4):

- Blood sample: 1x 6 mL purple top (DNA), 1x 8 mL PAXgene (RNA), 1x 10mL lavender top (plasma and PBMCs), 1x 3mL lavender top (CBC with diff), 1x 4mL Li Heparin (CMP)
- Vital signs: blood pressure, pulse, respirations, height, weight, etc.
- Dyspnea index
- 6-minute walk test
- Medication history
- EKG
- If tolerated, increase nebivolol dose to 10 mg once daily.
- Update medical record to reflect new dose.
- If possible, schedule Visit 3.
- Once complete, provide patient with compensation (\$40).

Phone Call 3 (week 5):

- How does patient feel compared to before starting study drug?
- Any perceived side effects?
- Provide results of safety assessment (everything looks similar to baseline OR significant difference in _____; the study physician recommends you _____.)

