- If not done already, schedule Visit 3.

Visit 3 (week 8):

- Blood sample: 1x 6 mL purple top (DNA), 1x 8 mL PAXgene (RNA), 1x 10mL lavender top (plasma and PBMCs), 1x 3mL lavender top (CBC with diff), 2x 4mL Li Heparin (nt-proBNP, CMP), 1x2.7mL blue top (INR)
- Vital signs: blood pressure, pulse, respirations, height, weight, etc.
- Dyspnea index
- Medication history
- 6-minute walk test
- EKG
- If possible, schedule Visit 4.
- Once complete, provide patient with compensation (\$40).

Phone Call 4 (week 9):

- How does patient feel compared to before starting study drug?
- Any perceived side effects?
- Provide results of safety assessment (everything looks similar to baseline OR significant difference in _____; the study physician recommends you _____.)
- If not done already, schedule Visit 4.

Visit 4 (week 18):

- Blood sample: 2x 8 mL PAXgene (RNA), 1x 10mL lavender top (plasma and PBMCs), 1x 3mL lavender top (CBC with diff), 2x 4mL Li Heparin (nt-proBNP, CMP), 1x2.7mL blue top (INR)
- Vital signs: blood pressure, pulse, respirations, height, weight, etc.
- Dyspnea index
- Medication history
- 6-minute walk test
- EKG
- Two-dimensional transthoracic echocardiogram (TTE) for research purposes
- RHC for research purposes (Appendix 1).
- Based on study physician recommendation, patients will be advised on how to proceed with beta-blocker treatment after the end of the study.
- Update medical records to indicate patient has completed study.
- Once complete, provide patient with final compensation (\$250).

Eligibility Criteria

Study Population. This study will include PH patients from Shands Hospital and UF Health pulmonary hypertension and cardiology clinics. Patients must be diagnosed with PH by right heart catheterization (RHC). This procedure is the gold-standard for PH diagnosis and is the most accurate way to measure the hemodynamics necessary to differentiate subtypes of PH. Inclusion criteria for this study include:

1. Adults (≥ 18 years of age) with World Health Organization Group 2 Pulmonary Hypertension:
 - a. Mean pulmonary artery pressure (mPAP) ≥ 25 mmHg,
 - b. And pulmonary capillary wedge pressure (PCWP) ≥ 15 mmHg or left ventricular end diastolic pressure (LVEDP) ≥ 15 mmHg

2. Evidence of either diastolic dysfunction on echocardiogram OR elevated filling pressures on invasive hemodynamic testing OR BNP>200 (NT-proBNP>220) pg/mL
3. NYHA class II-IV symptoms
4. Left ventricular ejection fraction (LVEF) \geq 45%

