Patients will be called 1 week after each dose change. BP and HR will be measured at each visit, as well as BMP, ECG, and LFT will be performed as safety assessments. Accumulated safety data will be reviewed by a study physician every six months to assess overall safety of nebivolol treatment.

Data Management

Patient data will be initially recorded using the patient data collection form and RHC data collection form. Patient data will then be transferred and stored using a custom-built REDCap database. REDCap is a secure, web-based application for building and managing online databases for the collection and entry of research data. Consents and other paper documentation will be kept in a locked cabinet in [name] locked, private office.

Risks and Benefits

Patients may not directly benefit. There is a potential benefit from improvements in progression of their PH. The potential risks include:

- Nebivolol: Risk of side effects such as: large decrease in blood pressure (less likely), headache (less likely), dizziness (less likely), nausea (rare), fatigue (rare), diarrhea (rare), difficulty breathing (very rare), and slow heart rate (very rare).
- Blood draws: discomfort at needle site (less likely), bruising at needle site (less likely), pain at site (less likely), swelling of vein (rare), fainting (rare), and infection (rare).
- Echocardiogram: no risks associated with this procedure
- Right heart catheterization: pain (less likely) or infection at catheterization sight (rare), vascular/valve damage (very rare), edema (rare), bruising (less likely), internal bleeding (very rare), blood clots (very rare), excessive fluid around the heart (very rare), and irregular heart rhythms (very rare).
- 6-minute walk distance: fatigue during walk (less likely)
- Accidental disclosure of PHI (rare)

Relevant Literature

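### The only cross-patient safety review runs on a six-month calendar, longer than one patient's 18-week course and not tied to how many patients have been dosed

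*Combined protocol and SAP*

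**What the plan says.** Safety Monitoring and Assessment sets the review across patients in one sentence: "Accumulated safety data will be reviewed by a study physician every six months to assess overall safety of nebivolol treatment". The text describes no monitoring committee, no study-level stopping rule and no other point at which data from several patients are examined together.

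Methods describes the study in these terms: "This project will be a prospective, open-label four-month clinical pilot study of 40 patients with PH and HFpEF". In the visit schedule, Visit 2 is at week 4 and Visit 4, with the final catheterization, is at week 18. The last planned increase is at Visit 2: "If tolerated, increase nebivolol dose to 10 mg once daily".

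For the individual patient, Safety Monitoring and Assessment adds: "Patients will be called 1 week after each dose change" and "BP and HR will be measured at each visit, as well as BMP, ECG, and LFT will be performed as safety assessments". The schedule places ECG, vital signs, metabolic panel and liver tests at baseline and weeks 4, 8 and 18, with calls at weeks 1, 2, 5 and 9.

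Statistical Methods refers twice to six months of nebivolol treatment, which does not agree with Methods or the visit schedule.

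**The concern.** A review of overall safety helps mainly by letting the experience of earlier patients inform what happens to later ones. Here the interval between reviews is longer than a patient's whole scheduled course, and it is fixed by the calendar rather than by the number of patients dosed. The faster the study enrols, the more patients are titrated between two reviews.

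The visits and calls judge one patient at a time. In a single-arm study of patients with NYHA class II-IV symptoms, one case of hypotension, bradycardia or worsening heart failure is hard to assign to drug or disease. A cluster after the week-4 step would be clearer in a table across patients, and the plan requires no such table until six months have passed. With fast enrolment, such a cluster could recur in many of the 40 patients before the first formal look.

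**Working it through.** The plan gives no calculation behind the six-month interval, so there is no figure of its own to reproduce.

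**Inputs from the protocol**
- Review interval R: six months, taken as 26 weeks (Safety Monitoring and Assessment).
- Last planned dose increase: week 4 (Visit 2). Last visit: week 18 (Visit 4).
- Number of patients: 40 (Methods).

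**Assumptions**
- Patients start evenly over time.
- The six-month clock runs from the first start; the protocol does not say.
- Dropout is ignored, as are patients who do not tolerate the increase.

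**Share with no review since their own first dose.** A patient passes a milestone at week T before the next review if the start falls in the first R − T weeks of an interval. The share is (R − T)/R and does not depend on enrolment speed.
- Passing week 4: (26 − 4)/26 = 85%.
- Finishing at week 18: (26 − 18)/26 = 31%.
- Finishing, with four months read as 16 weeks: (26 − 16)/26 = 38%.
- Finishing, with six months of treatment: (26 − 26)/26 = 0%. The 85% is unchanged.

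**A review between weeks 4 and 18.** That window is 14 weeks long. A review falls inside it for 14/26 = 54% of patients and does not for 46%.

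**Patients started before the first review.** This depends on enrolment, for which the protocol gives no period, so a range is shown. Under the present plan the number is 40 × 6/(enrolment months). With a trigger when the fifth patient reaches week 5, it is 5 plus those who start in the following 5 weeks, at 40/(enrolment weeks) per week.

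| Enrolment period | Present plan | With the trigger |
|---|---|---|
| 6 months (26 weeks) | 40 | 5 + 5 × 40/26 = 12.7 |
| 12 months (52 weeks) | 20 | 5 + 5 × 40/52 = 8.8 |
| 24 months (104 weeks) | 10 | 5 + 5 × 40/104 = 6.9 |
| 36 months (156 weeks) | 6.7 | 5 + 5 × 40/156 = 6.3 |

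The gain is large if enrolment is fast and almost nil if it is slow.

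**The case against.** The strongest reply is that six months is a legitimate choice for a small open-label pilot, and that nothing in the protocol contradicts it. Monitoring of individuals is frequent. The week-2 increase needs study-physician approval, every increase depends on tolerance, and the calls at weeks 5 and 9 return safety results with a study-physician recommendation where there is a significant difference. Unblinded staff may notice a recurring problem without a formal review. This largely stands, and it is why the point is an improvement rather than a fault. It does not replace a required tabulation. The individual layer also has loose ends to reconcile: a call is promised one week after each dose change, but none is scheduled at week 3, and no adverse-effect assessment is listed after week 9.

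A second reply is that the 85% and 31% overstate the exposure, because they count reviews since a patient's own first dose and ignore earlier reviews that already protect that patient. This also stands. With 24-month enrolment, 30 of 40 patients start after at least one review.

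Three stronger readings are tempting, and the documents do not support them.
- A reader might infer that nobody looks at safety for six months. The visits, tests and calls show otherwise.
- A reader might take Background and Significance to say that the drug's safety in these patients is unknown. What it calls unknown is the extent of haemodynamic improvement.
- A reader might infer that most of the 40 patients would be dosed before any review. That needs fast enrolment, and no enrolment period is given.

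**Conclusion.** The point holds in limited form. The one scheduled review across patients comes at intervals of about 26 weeks, against an 18-week course, and is not linked to exposure. With even starts, about 85% of patients pass week 4 and about 31% finish without a review since their own first dose. The 31% rests on the 18-week schedule and becomes about zero under the six months in Statistical Methods; Methods, the visit schedule and Statistical Methods must be reconciled. Between 10 and 40 patients start before the first review for enrolment periods of 24 down to 6 months, and fewer if enrolment is slower still.

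The weakness is confined to recognising a pattern across patients. It does not show that patients are unmonitored or that the six-month interval is an error. It matters most if enrolment is fast.

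**What to change.** In Safety Monitoring and Assessment, keep the six-month interval as a maximum and add an exposure trigger. The study physician reviews accumulated BP, HR, ECG, BMP, LFT and reported side effects, by visit against baseline, at whichever of these comes first:
- the first 5 patients have reached Call 3 (week 5) or have left the study earlier, and then each further 10 patients have done so;
- six months have passed since the last review.

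Each review ends with a dated record of its conclusion. Counting patients who leave early matters because the sample-size section allows for 30% attrition.

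The change adds at most four triggered reviews (after 5, 15, 25 and 35 patients). The data are already collected and stored in REDCap, and the reviewer's role already exists. The study is open-label and single-arm, and the review tests no efficacy hypothesis, so there is no cost in blinding or error rate. The price is one protocol sentence and a few more hours of study-physician time.

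Enrolment should not stop automatically for each review. The last patient of each block needs 5 weeks to reach Call 3, so holds at all four points would cost about 4 × 5 = 20 weeks.

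Two limits should be accepted. At 24-month enrolment, every further 10 patients is about every six months, so only the first look comes earlier. A first look at 5 patients is also weak: if an event had a 10% rate (an assumption), the chance of seeing two or more would be 1 − 0.9^5 − 5 × 0.1 × 0.9^4 = 8%.

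Separately, reconcile the treatment duration across Methods, the visit schedule and Statistical Methods.
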